October 19, 2019

Manuscript title: **Acute effects of High Intensity Interval Training (HIIT) and Steady State Moderate Intensity Training (SSMIT) on Intraocular Pressure among Sedentary Individuals.**

I am pleased to submit the manuscript entitled '*Acute effects of High Intensity Interval Training (HIIT) and Steady State Moderate Intensity Training (SSMIT) on Intraocular Pressure among Sedentary Individuals.*'

Intraocular pressure (IOP) remains the main treatable risk factor for glaucoma, which causes blindness in 4.5 million people worldwide, accounting for slightly more than 12% of all global blindness. Thus, treatment of glaucoma has traditionally been aimed at reducing the IOP, medically or surgically. Exercise is one of the factors that has been proven to influence IOP.

Our study investigated the effects of both forms of aerobic exercise on IOP in sedentary individuals. We believe that our findings would contribute valuable information for the use of exercise in the management of intraocular pressure. In addition, our study also provides useful information for future research on the effect of exercise in glaucoma management.

Sincerely,

DR [name]
Email: [contact]

RESEARCH PROTOCOL

Title of research: Acute effects of High Intensity Interval Training (HIIT) and Steady State Moderate Intensity Training (SSMIT) on Intraocular Pressure among Sedentary Individuals.

Overall the study can be divided into 3 phases :

Phase 1 : Recruitment Phase

Phase 2 : Baseline Assesment Phase

Phase 3 : Exercise Protocol Phase

Phase 1 : Recruitment Phase

1. Application to join the study will be open to all staff of University Malaya Medical Center.
2. 40 participants will be chosen based on the inclusion and exclusion criteria through a randomized method.
3. Consent, Patient Information Sheet and Global Physical Activity Questionnaire will be given and taken.

Inclusion criteria:

1. Healthy volunteers or patients able to undergo different intensity of exercise based on their VO₂max
2. Able to sign informed consent
3. Patients having medical problems to be well-controlled

Exclusion criteria

1. Previous ocular trauma
2. Previous surgery in the eligible eye
3. Known case of glaucoma/glaucoma suspect (IOP > 21mmHg)
4. History of glaucoma laser procedure/surgery within prior 6 months in eligible eye
5. Unable to undergo IOP measurements

6. Unable to give informed consent
7. Undiagnosed visual conditions
8. Uncontrolled medical condition such as:
 - end stage renal failure
 - uncontrolled diabetes
 - uncontrolled hypertension

Phase 2: Baseline Assessment Phase

Participants will do the assessment in the Sports Medicine Performance Lab

Baseline assessment parameters:

- Blood pressure
- Resting HR
- HRmax
- Body Impedance Analysis (BIA)
- Waist Circumference, Hip Circumference, Height
- VO₂max: 6 minute Astrand Rhythmic cycle ergometer test
- Baseline IOP

*For intraocular pressure assessment, all subjects will be measured at 10am (\pm 1hour) to avoid diurnal variation.

*Subjects are required to avoid any liquid/caffeinated drinks 1 hour prior to IOP measurement.

Phase 3 : Exercise Protocol Phase

[figure not shown]
1. The exercise sessions will be conducted in controlled room temperature (20-23C) between 8.00am to 11.00am using a Monarch 939E Bicycle Ergometer.
2. Participants are not allowed to drink water 2 hours prior until 30 minutes after the exercise session.
3. Each participant will perform both sessions (SSMIT & HIIT) based on the group they were assigned to with a 4 day wash out period between protocols.
4. Each protocol will have the participant cycle for 30 minutes at a speed of 60 rpm.
5. The SSMIT protocol: participants cycle at a moderate intensity of 50% of their VO₂R.

6. The HIIT protocol: consists of 10, 3-minute cycles (1 minute high intensity of 75% VO₂R and 2 minutes low intensity 35% VO₂R).
7. Participants HR will be monitored during the protocols using a HR monitor (Polar Heart Rate Monitor T31-Coded).
8. Before each session, the participants IOP of the right eye will be measured using an iCare rebound tonometer TA01i and repeated IOP measurements will be taken immediately after (0min), 5, 10, 15, 20 & 30 minutes after the exercise session.
9. Each IOP measurement will be taken on the participants right eye with them seated and contralateral eye focused on a distant object.
10. The examiner is blinded to which protocol the participant performed.

Schedule for phase 3:

Week 1: Group A (HIIT) & Group B (SSMIT) : 10 participants/day

Week 2: Group A (CME) & Group B (SSMIT) : 10 participants/day

Statistical Analysis

Data analysis will be conducted using Statistical Package for Social Studies (SPSS) software version 23.

Values for continuous variables are presented as means and standard deviation.

Prior to data analysis normality of continuous variable will be tested using skewness and kurtosis.

A two-way repeated measure ANOVA will be conducted to evaluate the effect of exercise on IOP and interaction between groups and time followed by using Bonferroni post-hoc test for pairwise comparison.

A paired sample T test will be conducted to assess the difference of IOP levels between interventions. A value of $p < 0.05$ is considered as significant.

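### The readable text randomises who is chosen, not who does HIIT or SSMIT first, and the paired t-test has no period term to protect the comparison

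*Combined protocol and SAP*

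**What the plan says.** Under Phase 1 : Recruitment Phase, item 2, "40 participants will be chosen based on the inclusion and exclusion criteria through a randomized method". The readable text does not mention randomisation again.

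Under Phase 3 : Exercise Protocol Phase, item 3, everyone does both protocols, "based on the group they were assigned to with a 4 day wash out period" separating them. How the groups are formed, how large they are, when they are formed and whether order is concealed are not stated. A figure at the head of Phase 3 is not shown in the copy reviewed.

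The Schedule for phase 3 has two lines. The first reads "Week 1: Group A (HIIT) & Group B (SSMIT) : 10 participants/day"; the second, for the following week, reads "Week 2: Group A (CME) & Group B (SSMIT) : 10 participants/day". Sessions run "between 8.00am to 11.00am using a Monarch 939E Bicycle Ergometer", with no rule for who gets which day or slot. For the IOP assessment in Phase 2, by contrast, the clock time is fixed at 10am, give or take an hour, "to avoid diurnal variation".

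The Statistical Analysis section compares the interventions with a paired t-test at 0.05. The two-way repeated-measures ANOVA beside it has groups and time as factors. Neither analysis names week (period) or order (sequence).

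**The concern.** Random selection from volunteers affects whom the results describe. It does not make the HIIT-versus-SSMIT comparison fair. In a two-period design that protection comes from random, balanced allocation to order and from an analysis that separates period from treatment. The readable text shows neither.

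Two things are at stake. First, a difference between the two weeks (season, familiarity with the tonometer or ergometer, device drift) either leaks into the HIIT-minus-SSMIT difference, if group sizes differ, or inflates its error term, if they do not. Second, if staff fill the diary by convenience, order can follow day or slot. The plan itself treats IOP as dependent on time of day, yet its exercise sessions span three hours.

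**Working it through.** **Inputs from the documents.** 40 participants; 10 per day; both groups cycle in both weeks; a window of 8 to 11 am (180 minutes); 30 minutes of cycling; IOP followed to 30 minutes afterwards; significance level 0.05 (sidedness not stated, taken as two-sided). The plan gives no power, effect size or SD, so the figure of 40 cannot be reproduced.

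**Assumptions.** Splits of 25/15 and 30/10; a week effect of 0.5 to 2 mmHg; an SD of 2 mmHg for within-person differences; a slot drift of 0.25 to 1 mmHg per hour. None of these is in the documents.

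**1. Bias from week.** Let d be HIIT minus SSMIT, T the true difference, and w the week 1 minus week 2 effect. In a clean two-order crossover:

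- HIIT-first: mean d = T + w
- SSMIT-first: mean d = T - w
- Crude paired mean = T + w x (nA - nB)/40

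| Split | (nA - nB)/40 | Bias at w = 0.5 / 1 / 2 mmHg |
|---|---|---|
| 20/20 | 0 | 0 / 0 / 0 |
| 25/15 | 10/40 = 0.25 | 0.125 / 0.25 / 0.5 |
| 30/10 | 20/40 = 0.50 | 0.25 / 0.5 / 1.0 |

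For scale, 40 pairs detect 0.454 SD with 80% power, which is 0.454 x 2 = 0.91 mmHg.

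**2. Error term at 20/20.** The week effect leaves the mean but stays in the spread. With w = 1, the expected variance of d rises from 4 to 4 + 1 x 40/39 = 5.03, so the SD goes from 2 to 2.24. On that SD the detectable difference is 0.454 x 2.24 = 1.02 mmHg instead of 0.91.

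**3. Type I error of the paired t-test** (simulated, 20,000 runs, SD 2 mmHg). With no week effect it is about 0.05. With w = 1 it is about 0.03 at 20/20, 0.08 at 25/15 and 0.28 at 30/10.

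**4. Groups that are not comparable.** If the week effect is wA in one group and wB in the other, the bias is (nA x wA - nB x wB)/40. At 20/20 this is (wA - wB)/2, so equal sizes alone do not remove it. Random allocation makes wA and wB equal in expectation.

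**5. Slot.** Cycling plus follow-up takes at least 30 + 30 = 60 minutes. If follow-up falls inside the window, one station handles 180/60 = 3 people and ten people need 4 stations. Unless there are ten stations, slots must differ between people. A slot that is the same at both of a person's sessions cancels in d. Bias arises when HIIT sessions sit, on average, at a different hour from SSMIT sessions, and it equals shift x drift: from 0.5 h x 0.25 = 0.125 mmHg to 2 h x 1 = 2 mmHg in raw IOP. A 0.5 mmHg slot bias at 20/20 gives a simulated type I error of about 0.34.

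**6. Why blocking is needed.** Unrestricted coin-flip allocation gives 25/15 or worse with probability 2 x P(Binomial(40, 0.5) <= 15) = 0.154. Simple randomisation would not secure 20/20.

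**7. What a period term does.** Averaging the two group means gives ((T + w) + (T - w))/2 = T for any group sizes, and the week effect leaves the error term.

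**8. Limit of the algebra.** Steps 1 to 4 and 7 assume that each person does both protocols, in one of two orders. The printed Week 2 line shows an undefined CME for Group A, SSMIT again for Group B, and no HIIT. That contradicts item 3.

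**The case against.** The Phase 3 figure, where allocation would naturally be drawn, is not available, and it may show random order. Phase 1, item 2 may also be loose wording for random allocation. Each person is their own control, and IOP is taken before each session (item 8), so change scores would remove part of a day or slot offset. Nothing in the text suggests unequal groups, and every effect size above is assumed.

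Most of this stands, and it limits the point: the text leaves the protection unstated, which is not proof that it was absent. It does not rescue the analysis. The Statistical Analysis section is fully readable, has no period term and does not say that change scores are used.

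Three stronger readings are tempting, and the documents do not support them:

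- A reader might infer that order is confounded with week. Both groups cycle in both weeks, so it is not. Treatment is mixed with week only if group sizes or week effects differ between groups, or on the Week 2 line exactly as printed.
- A reader might infer that exclusions in Phase 2 unbalance the groups. Eligibility is applied when the 40 are chosen, groups first appear in Phase 3, and no text says they are formed earlier.
- A reader might infer that whole days go to one group and reveal the protocol to the examiner. The schedule lists both groups together at "10 participants/day", and item 10 states that the examiner is blinded.

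**Conclusion.** The point holds as a gap in the readable design and a weakness in the stated analysis. Random allocation to order, group sizes, and day and slot balance are not stated, and the figure may supply some of them. The paired t-test ignores period, whatever the figure shows.

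The size depends on what was done. In a clean crossover at 20/20, a common week effect causes no bias but makes the test conservative (type I error about 0.03 for an assumed 1 mmHg week effect and 2 mmHg SD). At an assumed 25/15 or 30/10, a quarter or a half of the week effect enters the estimate. A mean slot difference between protocols could add bias in raw IOP, in proportion to an hourly drift that the documents do not give. This deserves correction. It is not evidence that the comparison was in fact biased.

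**What to change.** - **Allocation.** State that order (HIIT-first or SSMIT-first) is allocated 1:1 from a computer-generated list once eligibility is confirmed. Block it so that each ten-person day has 5 of each group; four days (40/10) then give 20/20. Conceal it until the first session and keep it from the IOP examiner. If the Phase 3 figure already shows random order, only the missing details need adding.
- **Slot.** Keep each participant's clock slot the same at both sessions.
- **Analysis.** Replace the plain paired t-test with a crossover analysis that includes period and sequence, and use the pre-session IOP already collected, for example as change from pre-session.
- **Schedule.** Reconcile the Week 2 line with Phase 3, item 3, and define or remove the abbreviation CME.

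The cost is one list, a few sentences of protocol text and a slightly different model. No visits, staff or participants are added. The small downside is less freedom in booking.

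### Eligibility neither restricts nor records medication, so a participant on a heart-rate-limiting drug could have both sessions set harder than the stated percentage of VO₂R

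*Combined protocol and SAP*

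**What the plan says.** Phase 1, inclusion criterion 1 opens the trial to "Healthy volunteers or patients able to undergo different intensity of exercise based on their VO₂max". Criterion 3 adds "Patients having medical problems to be well-controlled". The medical exclusion begins "Uncontrolled medical condition such as", and its listed examples include "uncontrolled hypertension". The eye-related exclusions include "Known case of glaucoma/glaucoma suspect (IOP > 21mmHg" but name no drugs.

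Phase 2 lists one source of aerobic capacity: "VO₂max: 6 minute Astrand Rhythmic cycle ergometer test". Resting HR and HRmax are also baseline parameters, with no method given for HRmax.

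Phase 3 sets SSMIT at 50% of VO₂R (item 5) and HIIT at "1 minute high intensity of 75% VO₂R and 2 minutes low intensity 35% VO₂R" (item 6). Item 7 says "Participants HR will be monitored during the protocols using a HR monitor"; no rule links the reading to the workload. The only intake limits in Phases 2 and 3 concern drinks and caffeine.

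**The concern.** The protocol controls time of day, fluids, caffeine and room temperature, but is silent on medication. That matters because both interventions are defined by relative intensity, and relative intensity appears to depend on a test that infers VO₂max from heart rate at a submaximal load. A drug that lowers heart rate at a given load makes the participant look fitter than they are, so every workload derived from the estimate is too high. The monitor worn during the session would not reveal this reliably, because the same drug holds its reading down.

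For such a participant the sessions would not be the intensities the trial names. A person under treatment for a cardiovascular condition could also work harder than intended without heart rate showing it.

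**Working it through.** **1. Entry rules.** Controlled conditions are admitted and uncontrolled ones excluded. Treated, controlled hypertension therefore qualifies whatever the drug class. Excluding known glaucoma and glaucoma suspects removes most users of pressure-lowering eye drops, but not users of systemic drugs taken for another condition. No drug exclusion, drug record or stable-dose rule was found. One Phase 3 figure was not available to this check.

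**2. From test to workload.** The documents do not say how VO₂R is derived. The link is inferred: the Astrand test is the only VO₂max measure, and criterion 1 ties intensity to VO₂max. That the test works from submaximal heart rate is general knowledge of the method, not a statement in the documents.

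**3. Illustration.** The plan has no figure to reproduce. Only the 35%, 50% and 75% labels come from the documents. All other inputs are assumptions: true VO₂max 2.5 L/min, resting VO₂ 0.25 L/min, a test load at 50% of VO₂R, and straight-line extrapolation of heart rate.

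- True VO₂R = 2.5 − 0.25 = 2.25 L/min. VO₂ at the test load = 0.25 + 0.5 × 2.25 = 1.375, which is 1.125 above rest.
- Estimated VO₂R = 1.125 ÷ [(HR − rest) ÷ (HRmax − rest)].
- Ratio = estimated VO₂R ÷ 2.25. True intensity = label × ratio.
- Off drug with HRmax 185, heart rate at this load is 122.5 (rest 60) or 127.5 (rest 70), and the ratio is 1.

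| Rest | HR at load, on drug | HRmax used | Ratio | 35% becomes | 50% becomes | 75% becomes |
|---|---|---|---|---|---|---|
| 60 | 120 | 185 | 1.04 | 36.5% | 52.1% | 78.1% |
| 60 | 110 | 185 | 1.25 | 43.8% | 62.5% | 93.8% |
| 70 | 120 | 185 | 1.15 | 40.3% | 57.5% | 86.3% |
| 70 | 110 | 185 | 1.44 | 50.3% | 71.9% | 107.8% |
| 60 | 110 | 160 | 1.00 | 35.0% | 50.0% | 75.0% |
| 60 | 110 | 150 | 0.90 | 31.5% | 45.0% | 67.5% |

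Example, second row: 1.125 ÷ (50 ÷ 125) = 2.81, and 2.81 ÷ 2.25 = 1.25.

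The last two rows use an HRmax measured on the drug. There the error disappears or reverses.

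**4. Effect on the contrast.** With rest 60 and HRmax 185, all labels scale by 1.04 to 1.25. The gap between the high and low HIIT phases grows from 75 − 35 = 40 points to between 41.7 and 50. The HIIT session average is (75 + 2 × 35) ÷ 3 = 48.3%, against 50% for SSMIT. That difference of 1.7 points grows only to between 1.7 and 2.1.

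**5. How many participants.** The documents give no figure. If 2%, 5% or 10% of entrants used such a drug (assumed), the expected number among 40 is 0.8, 2 or 4. The chance of at least one, 1 − (1 − p)^40, is 55.4%, 87.1% or 98.5%. Even if every user sat at the 93.8% end, the mean labelled-75% intensity over all 40 would rise by 18.75 × 0.8/40 = 0.4, 18.75 × 2/40 = 0.9 or 18.75 × 4/40 = 1.9 points.

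**The case against.** The strongest reply is the design. Each participant does both sessions, IOP is taken before each one, and the interventions are compared by paired t test and repeated-measures ANOVA. A reader might infer that a drug-lowered resting IOP biases the HIIT-SSMIT comparison. The documents do not support that: a stable effect on resting IOP largely cancels within the person. One VO₂max estimate also serves both sessions, so the order of the intensities is kept. This part of the objection stands. It does not cover the proportional error in absolute intensity, or an IOP response to exercise that the drug itself may change.

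A second reply concerns direction. A reader might infer that the test always overstates VO₂max in these participants. Under the formula above that depends on HRmax, whose method is not stated: a value measured on the drug could remove or reverse the error. This stands, and the conclusion is conditional on it.

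A third concerns size. A reader might infer that the high-intensity bout would exceed true capacity, as in the 107.8% row. That row needs resting heart rate to stay at 70 while heart rate at the test load falls from 127.5 to 110. If rest falls to 60 as well, the result is 93.8%. The documents list resting HR as a baseline measurement, so it would be taken on the drug. They give no basis for a figure above 100%.

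Finally, few participants may be affected. That limits the effect on group means, as step 5 shows, but not the concern for an individual participant.

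**Conclusion.** The gap is real. Followed as written, the protocol can enrol a user of a heart-rate-limiting drug, would not record that use, and may set both sessions from an inflated capacity estimate. If HRmax is age-predicted or taken off drug, the illustration puts a labelled 75% bout at about 78% to 94% of true VO₂R and a labelled 50% session at about 52% to 63%, with resting heart rate 60. Larger errors need less consistent assumptions.

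The consequence is mislabelled intensity, a wider high-low contrast and a possibly altered IOP response in the affected participants, plus an individual safety concern because the monitor is blunted too. The effect on the average comparison is probably small, and the documents do not support calling the HIIT-SSMIT contrast invalid. Confidence is medium: the number of users, the HRmax method and the VO₂R derivation are all unstated.

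**What to change.** - Add an exclusion in Phase 1 for current use of systemic heart-rate-limiting drugs, naming systemic beta-blockers. A wider clause covering any drug that might alter IOP would be open-ended and is not needed.
- Add one medication question at recruitment. The forms listed there are consent, an information sheet and an activity questionnaire, and none is shown to collect this.
- Record other medication with the Phase 2 baseline parameters, and state there how HRmax and VO₂R are obtained, because the direction of the error depends on it.
- The cover letter describes the study in the past tense. If enrolment is already complete, report medication use and add a sensitivity analysis that repeats the main comparison without users of such drugs.

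The cost is one criterion, one question and a baseline entry, with no new procedure. A few treated staff become ineligible, and the results generalise slightly less widely.

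### A participant's HIIT and SSMIT sessions need not share a clock time, so time of day adds avoidable noise to the paired comparison of IOP

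*Combined protocol and SAP*

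**What the plan says.** The asterisked note under Phase 2 (Baseline Assessment Phase) begins "For intraocular pressure assessment, all subjects will be measured at 10am", allows one hour either side, and gives avoidance of diurnal variation as the reason.

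Phase 3 (Exercise Protocol Phase) sets a different window. Item 1: "The exercise sessions will be conducted in controlled room temperature (20-23C) between 8.00am to 11.00am using a Monarch 939E Bicycle Ergometer". Item 3 has every participant perform both protocols, four days apart. Item 4: "Each protocol will have the participant cycle for 30 minutes at a speed of 60 rpm". Item 8 takes IOP before the session and then, "repeated IOP measurements will be taken immediately after (0min), 5, 10, 15, 20 & 30 minutes after the exercise session", which makes seven readings per session. The schedule line for week 1 reads "Week 1: Group A (HIIT) & Group B (SSMIT) : 10 participants/day".

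The Statistical Analysis section plans a two-way repeated measures ANOVA with a group-by-time interaction and, separately: "A paired sample T test will be conducted to assess the difference of IOP levels between interventions". It does not mention the session's own pre-exercise value or the clock time.

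**The concern.** The plan identifies a nuisance factor, controls it at baseline, and on the visible text leaves it uncontrolled where the outcome is measured. Two things are missing: a statement of whether the 10am rule governs the Phase 3 readings, and a rule tying a participant's two sessions to the same time of day.

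The second matters more. In a crossover each participant is his or her own control, so a time-of-day effect cancels only if both sessions are at the same time. If one is early and the other late, the drift between those times goes straight into the HIIT-SSMIT difference and inflates its variance. If slots also differed systematically by protocol, the result would be bias; the text neither states nor rules that out.

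**Working it through.** The documents give no SD, effect size, power or diurnal slope, so there is no figure of the plan's own to reproduce.

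**From the documents:** n = 40; session window 8.00 to 11.00; 30-minute rides; 10 participants per day; seven readings, at the start and at 30 + (0, 5, 10, 15, 20, 30) minutes after it.

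**Assumed:** linear drift b of 0.25 to 1.0 mmHg per hour; SD of the paired difference 3 mmHg (also 2 and 4); start times independent between the two sessions; no changeover time between rides.

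**1. Must starts be spread?** One ergometer fits 180/30 = 6 rides in the window, fewer than 10. Ten simultaneous starts would need ten ergometers; the number is not given. With 2, 3, 4 or 5 ergometers, 10 per day needs 5, 4, 3 or 2 half-hour starts.

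**2. Readings outside 9.00 to 11.00, if the Phase 2 rule applied.**

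| Start | Outside, of 7 |
|---|---|
| 8.00 | 6 |
| 8.30 | 1 |
| 9.00, 9.30, 10.00 | 0 |
| 10.30 (only if the follow-up may run past 11.00) | 5 |

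With two ergometers and starts from 8.00 to 10.00, 4 of 10 participants are affected, and 2 × (6 + 1) = 14 of 70 readings per day fall outside.

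**3. Noise from unmatched times.** For two independent uniform starts over R hours, the gap has SD R/√6. The last start is 10.00 if the follow-up must end by 11.00 and 10.30 if only the ride must, so R = 2.0 to 2.5 and the gap SD is 0.82 to 1.02 h. The added SD is c = b × gap SD = 0.20 to 1.02 mmHg, and SE = √(SD² + c²)/√40.

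| SD (mmHg) | SE, matched | SE, unmatched | Rise |
|---|---|---|---|
| 2 | 0.316 | 0.318 to 0.355 | 0.5% to 12.3% |
| 3 | 0.474 | 0.475 to 0.501 | 0.2% to 5.6% |
| 4 | 0.632 | 0.633 to 0.653 | 0.1% to 3.2% |

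At SD 3 this is worth c²/9 = 0.5% to 12% more participants. Take an effect giving 80% power (paired t, two-sided 0.05) when times match. Unmatched power is then 79.8% to 75.6% at SD 3 and 79.6% to 70.4% at SD 2.

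**4. Dependence on equipment.** Half-hour slots on 2, 3, 4 or 5 ergometers give a gap SD of 1.00, 0.78, 0.59 or 0.35 h. At 1.0 mmHg per hour and SD 3 the rise is 5.4%, 3.3%, 1.9% or 0.7%, and nil with ten.

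**5. Matching within 30 minutes.** A gap uniform on ±0.5 h has SD 1/√12 = 0.289 h, so c = 0.07 to 0.29 mmHg. At SD 3 the SE is 0.4745 to 0.4765, a rise of 0.03% to 0.5%.

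**6. Using the pre-exercise reading.** Let r0 be the correlation between the pre- and post-exercise HIIT-SSMIT differences without clock noise, both with SD 3. Put V = 9 + c² and r = (9·r0 + c²)/V. Then SE(level) = √(V/40); SE(change) = √(18(1 − r0)/40), because the common offset cancels; and SE(adjusted) = √(V(1 − r²)/40 × (1 + 1/37)).

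| Case | Level | Change | Adjusted |
|---|---|---|---|
| c = 1.0, r0 = 0 | 0.500 | 0.671 | 0.504 |
| c = 1.0, r0 = 0.33 | 0.500 | 0.549 | 0.465 |
| c = 1.0, r0 = 0.5 | 0.500 | 0.474 | 0.423 |
| matched, c = 0.29, r0 = 0.33 | 0.477 | 0.549 | 0.455 |

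A simulation of 40,000 trials for the second row gave 0.499, 0.548 and 0.463. If the two differences are uncorrelated, the covariate costs √(38/37) − 1 = 1.3%; it breaks even at r = √(1/38) = 0.16.

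**The case against.** The 10am note sits under Phase 2 beside the baseline list, and Phase 3 sets its own conditions. Its companion note on drinks (one hour before IOP) likewise gives way to a two-hour rule in Phase 3, which suggests that the notes cover Phase 2 only. On that reading there is no conflict of windows, and the counts in step 2 show no fault: a participant riding at 8.00 both times is outside the window yet perfectly matched. This is a fair reading. It is why the request is first for a statement of scope; the missing matching rule stands either way.

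The size is driven by assumptions, and the upper end needs the largest drift, the widest spread and independent starts together. This stands. At 0.5 mmHg per hour and SD 3 the rise is only 0.9% to 1.4%.

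The group-by-time interaction in the ANOVA is untouched by linear drift. This also stands, but the paired t test on levels is planned separately and has no such protection as described. The plan does not say which time points enter it.

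The Phase 3 figure is not available and could hold scheduling detail. If it matches slots, one sentence in the text settles the matter.

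Finally, covariate adjustment gains precision mostly for reasons unrelated to clock time. True once sessions are matched. It is still the natural guard against whatever mismatch remains, and uses data already collected.

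**Conclusion.** The concern holds. The visible text controls time of day at baseline but does not match it within participant for the comparison of interest, and the paired t test as described does not remove the resulting noise. The loss is one of precision, small to moderate: 0.2% to 5.6% in standard error at SD 3, up to 12.3% at SD 2, and nil if all ten participants ride at once. These figures rest on assumed drift, SD, number of ergometers and independent starts. No bias is expected unless slots differ by protocol. The point should be acted on because the remedy is almost free; it does not invalidate the design.

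**What to change.** 1. State whether the 10am ±1 hour rule governs Phase 3 readings, and reconcile it with the 8.00 to 11.00 session window.
2. Book each participant's two sessions at the same clock time, within 30 minutes, and record the clock time of every reading.
3. In the HIIT-versus-SSMIT contrast, adjust for the pre-exercise HIIT-SSMIT difference as a covariate. Do not substitute an unadjusted change score, which is noisier than levels when the two differences correlate below 0.5 (ignoring clock noise).

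**Cost:** a booking rule, one recorded time per reading and one sentence in the analysis section. Booking is slightly less flexible, but same-slot matching uses no extra capacity. The covariate costs about 1.3% in standard error if it proves uninformative. If the sponsor applies the 10am rule to Phase 3, only the 9.00, 9.30 and 10.00 half-hour starts remain. Ten per day then needs four ergometers; with two, capacity is 3 × 2 = 6 per day, so 40 participants take 7 days per period instead of 4.

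### The Week 2 schedule line gives Group B SSMIT a second time and Group A an undefined 'CME', contradicting the rule that everyone does both protocols

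*Combined protocol and SAP*

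**What the plan says.** All the relevant text is in the combined protocol and SAP.

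- **Phase 3, item 3** sets the design rule: "Each participant will perform both sessions (SSMIT & HIIT) based on the group they were assigned to", "with a 4 day wash out period between protocols".
- **Phase 3, items 5 and 6** define two protocols and no third: "The SSMIT protocol: participants cycle at a moderate intensity" and "The HIIT protocol: consists of 10, 3-minute cycles".
- **Schedule for phase 3** assigns protocols by week: "Week 1: Group A (HIIT) & Group B (SSMIT) : 10 participants/day", followed by "Week 2: Group A (CME) & Group B (SSMIT) : 10 participants/day".
- **Statistical Analysis** plans a paired t-test of IOP between the interventions. It also plans a repeated-measures model: "A two-way repeated measure ANOVA will be conducted to evaluate the effect of exercise on IOP and interaction between groups and time".
- **Phase 1, item 2** gives 40 participants. No split between Groups A and B is stated.

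**The concern.** The schedule is the only readable text that says which group does which protocol in which week. Item 3 requires both protocols but gives no order. If the schedule is wrong, a reader cannot tell what sequence each group received.

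Two things depend on that sequence. The paired t-test needs one HIIT and one SSMIT session from each participant, and a group that did SSMIT twice supplies no pair. The sequence also decides whether protocol is balanced against week. With opposite orders in equal groups, a week effect cancels from the HIIT-versus-SSMIT difference. With a single order, it is inseparable from the protocol effect.

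Only the HIIT-versus-SSMIT comparison is at stake, though that is the comparison named in the title. The change in IOP over time within a session could still be analysed, because item 8 takes a reading before exercise and "repeated IOP measurements will be taken immediately after (0min), 5, 10, 15, 20 & 30 minutes after the exercise session". That makes 1 + 6 = 7 readings per session. If 'groups' in the ANOVA means the two protocols as a within-participant factor, its interaction with time would rest on the same reduced set of pairs.

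**Working it through.** **Step 1: set the texts side by side.** The plan has no sample-size or power figure to reproduce, so the main check is textual.

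| | Week 1 | Week 2 | Both protocols done? |
|---|---|---|---|
| Group A, as scheduled | HIIT | CME (undefined) | only if CME means SSMIT |
| Group B, as scheduled | SSMIT | SSMIT | no |
| Group A, item 3 with Week 1 as written | HIIT | SSMIT | yes |
| Group B, item 3 with Week 1 as written | SSMIT | HIIT | yes |

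The Group B row conflicts with item 3 whatever CME means.

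**Step 2: find the corrections that would satisfy item 3.**

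1. The Week 1 line is right, and Week 2 should be Group A SSMIT, Group B HIIT.
2. Group B's Week 1 entry should be HIIT and CME means SSMIT, so both groups do HIIT then SSMIT. This is less plausible, because two groups would then serve no purpose.

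**Step 3: count the pairs.** Assume a 20/20 split of the 40.

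- Item 3 followed: 40 pairs.
- Schedule followed literally, CME means SSMIT: 20 pairs, all from Group A.
- Schedule followed literally, CME means something else: 0 pairs.

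**Step 4: precision, as an illustration of literal execution with CME meaning SSMIT.** The half-width of the 95% confidence interval for the mean paired difference, in units of the SD of the paired differences, is t(0.975, n − 1)/√n. The detectable effect also assumes a two-sided 0.05 paired t-test with 80% power (noncentral t); the plan states neither the power nor the sidedness. The rows for 15 and 25 pairs show the effect of an unequal split.

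| Pairs | Half-width (SD) | Detectable effect (SD) |
|---|---|---|
| 40 | 2.0227/6.325 = 0.320 | 0.454 |
| 25 | 2.0639/5 = 0.413 | 0.584 |
| 20 | 2.0930/4.472 = 0.468 | 0.660 |
| 15 | 2.1448/3.873 = 0.554 | 0.778 |

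The ratio of half-widths for 20 against 40 pairs is 1.46.

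**Step 5: week effect.** Let τ be the true HIIT-minus-SSMIT difference and w the Week 2 minus Week 1 effect on the outcome compared. A participant in the order HIIT then SSMIT contributes τ − w. One in the opposite order contributes τ + w. With nA and nB participants in these two orders, the bias of the mean is

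w(nB − nA)/(nA + nB).

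- Opposite orders, 20/20: w(20 − 20)/40 = 0.
- Opposite orders, 15/25 or 25/15: ±10w/40 = ±0.25w.
- All pairs HIIT then SSMIT (correction 2 with 40 pairs, or the literal schedule with 20): −w.

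The documents give no size for w.

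**The case against.** The strongest reply is that this is a typing error with no consequence. The title, items 3, 5 and 6, and the paired test all describe two protocols per participant, and nothing readable shows that anyone followed the Week 2 line. The precision figures need literal execution, an equal split and CME meaning SSMIT all at once, and the power figures add an assumed 80%. They show only what halving any paired sample does. This is fair. The figures are an illustration and not an estimate of harm done.

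Second, a figure in Phase 3 is not shown and may define CME or display the intended sequence. That also stands: CME can be called undefined only in the readable text. The figure could answer the question put to the investigator, but it cannot make the written Week 2 line agree with item 3 for Group B.

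Third, IOP is measured before each session, so a constant week-to-week shift in IOP level cancels from the change since the pre-exercise reading and from a protocol-by-time interaction. This is correct and narrows the bias. The −w applies when raw IOP levels are compared, as the paired test may do, or when the week alters the response to exercise itself.

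What survives is that two operative statements conflict, and no other readable text gives the order.

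**Conclusion.** The contradiction is certain; its consequence is conditional. As written, Group B never performs HIIT and Group A performs something undefined, so the schedule cannot be reconciled with item 3.

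If item 3 was followed with opposite sequences, nothing is lost and only the text is wrong. This is the most likely case. If the schedule was followed literally, a 20/20 split and CME meaning SSMIT would leave 20 pairs instead of 40. The interval half-width would rise from 0.32 to 0.47 SD, and the effect detectable with 80% power from 0.45 to 0.66 SD. Any week effect on the outcome compared would pass in full into the protocol difference. If CME is not SSMIT, the planned paired comparison could not be made at all.

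This should be fixed: the main comparison depends on the answer, and clarification costs almost nothing.

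**What to change.** The investigator should first confirm the intended sequence. If the Week 1 line is right, Week 2 should list Group A under SSMIT and Group B under HIIT at the same 10 participants per day, with CME removed. If CME is an older name for one of the two protocols, say which.

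The cover letter, dated October 19, 2019, already speaks of findings, so the sessions appear to have been run. The correction should therefore be a dated clarification and not a silent edit. It should state the sequence each group actually received and the number of participants who completed both protocols. The paired t-test should be described as using those participants only.

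If item 3 was followed, the cost is one corrected line and one sentence on the sequence given, with no extra participants or visits. If the schedule was followed literally, correcting the text does not recover Group B's missing HIIT sessions (20 under the assumed split). The smaller number of pairs and the single order must then be reported as limitations of the comparison.
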